7.1.4.2 Dose Modifications and Toxicity Management for Vopratelimab in Combination with Nivolumab

For dose modifications for nivolumab please follow the prescribing information ([Opdivo® Full Prescribing Information {Bristol-Myers Squibb Company 2021}](#)). In the event of a toxicity that requires that study treatment be withheld until resolution to Grade 0 or 1, the first administration of study drug after resolution of toxicity should be vopratelimab alone. Nivolumab may be added at the next dose, at the discretion of the investigator and the medical monitor, if the toxicity does not recur with vopratelimab monotherapy.

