6 STUDY TREATMENTS AND ADMINISTRATION

6.1 Study Drug Dosage and Administration

For this study, the investigational drug refers to vopratelimab, which will be supplied by the Sponsor, Jounce Therapeutics. Study drug(s) refer to vopratelimab and any partner drugs administered in the parent study (e.g., nivolumab, ipilimumab).

All dosages prescribed and dispensed to subjects and all dose changes during the study must be recorded on the Dosage Administration Record electronic case report form (eCRF).

For all study medication administration, a physician must be present at the site or immediately available to respond to emergencies during all administrations of all study medications. Note that the infusion time is not inclusive of the flush post study drug administration.

Vopratelimab is administered as a single agent or in combination with nivolumab or in sequence with ipilimumab at a subject's prior identified tolerable dose regimen and schedule. Any changes to the dose and schedule of the study agents must be discussed with the medical monitor as stated in [Section 3](#).

When vopratelimab is administered on the same day as nivolumab, vopratelimab should be dosed first with a 30-minute (-5/+10 minutes) evaluation period prior to administration of combination therapy. In instances where an infusion reaction occurs during dosing of vopratelimab, administration of combination therapy may be delayed beyond the 30-minute (-5/+10 minutes) evaluation period.

If treating in sequence with ipilimumab, continue to follow dosing guidelines from the parent study for up to 4 doses. Administer ipilimumab as a 90-minute IV infusion or per the approved label infusion time (-5/+10 minutes) at a dose of 3 mg/kg q6w for up to 4 doses. Note that the approved schedule for ipilimumab administration is q3w; this protocol administers ipilimumab at a less frequent schedule. Additional doses of ipilimumab beyond 4 doses total may be considered on a patient by patient basis in consultation with the medical monitor.

Further instructions for the preparation and dispensation of vopratelimab, nivolumab, and ipilimumab are described in the Study Pharmacy Manual.

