| | Grade 3 | 
 Permanently discontinue ipilimumab/nivolumab. Withhold vopratelimab until resolution to Grade 0-1. When symptoms resolve to Grade 0-1, resume vopratelimab.^b If symptoms persist 2¹ 6 weeks, or subject is unable to reduce the corticosteroid dose to less than 7.5 mg prednisone or equivalent per day, discuss subject continuation with the Medical Monitor.^b | 1-2 mg/kg/day prednisone equivalents followed by steroid taper ^a If symptoms persist 2 ¹ 3-5 days or recur after improvement, consider administering IV corticosteroid or noncorticosteroid ^a |
| | Grade 4 | 
 Permanently discontinue study drug(s). | 1-2 mg/kg/day prednisone equivalents followed by steroid taper ^a Administer IV corticosteroid until symptoms improve to grade 1 ^a Consider early infliximab 5-10 mg/kg if symptoms refractory to corticosteroid within 2-3 days ^a |

| Adverse Event | Toxicity Grade | Dose Modification | Recommended Management ^a |
|---------------|--|--|---|
| Pneumonitis | Grade 2 | 
 Withhold study drug(s) until resolution to Grade 0-1. When symptoms resolve to Grade 0-1, resume vopratelimumab only. If symptoms do not recur after 1 cycle of vopratelimumab, resume combination therapy.^b Permanently discontinue ipilimumab/nivolumab if symptoms last 6 weeks or longer. | 1-2 mg/kg/day prednisone equivalents followed by steroid taper ^a |
| | Grade 3 or 4 | 
 Permanently discontinue study drug(s). | 1-2 mg/kg/day prednisone equivalents followed by steroid taper If no improvement after 48 hours, may add infliximab 5 mg/kg or mycophenolate mofetil IV 1 g twice a day or IVIG for 5 days or cyclophosphamide ^a Empirical antibiotics |
| Hepatitis | Grade 2 AST/ALT (>3 to 5 × ULN) or bilirubin (1.5 to 3 × ULN) ^b | 
 Withhold study drug(s) until resolution to Grade 0-1. When symptoms resolve to Grade 0-1, resume vopratelimumab only. If symptoms do not recur after 1 cycle of vopratelimumab, resume combination therapy.^b Permanently discontinue ipilimumab/nivolumab if symptoms last 6 weeks or longer. | 0.5 to 1 mg/kg/day prednisone equivalents or investigator discretion ^a |

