| | Grade 3: serum creatinine (> 3 to $6 \times$ ULN) | 
 Permanently discontinue study drug(s). | 
1-2 mg/kg/day prednisone equivalents^a
 
Consult nephrology
 
Evaluate for other causes (recent IV contrast, medications, fluid status, etc)
 
If improved to Grade 1, taper corticosteroids over at least 4 weeks
 
If elevation persists >3-5 days or worsen, consider additional immunosuppression (e.g. – mycophenolate)
 |
| | Grade 4: serum creatinine ($> 6 \times$ ULN) | 
 Permanently discontinue study drug(s). | 
1-2 mg/kg/day prednisone equivalents^a
 
Consult nephrology
 
Evaluate for other causes (recent IV contrast, medications, fluid status, etc)
 
If improved to Grade 1, taper corticosteroids over at least 4 weeks
 
If elevations persist >2-3 days or worsen, consider additional immunosuppression (e.g. – mycophenolate)
 |
| Rash | Grade 2 | 
 Withhold study drug(s). When symptoms resolve to Grade 0-1, resume vopratelimab. If symptoms do not recur after 1 cycle of vopratelimab, resume ipilimumab/nivolumab.^b | 
Should treat skin with topical emollients, oral antihistamines, and medium- to high-potency topical corticosteroids.
 
0.5 to 1 mg/kg/day prednisone equivalents^a
 |
| | Grade 3 | 
 Withhold study drug(s) until resolution to Grade 0-1. When symptoms resolve to Grade 0-1, resume vopratelimab only; permanently discontinue ipilimumab/nivolumab. | 
Should treat skin with topical emollients, oral antihistamines, and high-potency topical corticosteroids.
 
1-2 mg/kg/day prednisone equivalents^a
 |
| | Grade 4 | 
 Permanently discontinue study drug(s). | 
1-2 mg/kg/day prednisone equivalents^a
 
Admit for inpatient management
 |

| Adverse Event | Toxicity Grade | Dose Modification | Recommended Management ^a |
|---------------|---|---|---|

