| Uveitis, iritis | Grade 2 | 
 Withhold study drug(s). When symptoms resolve to Grade 0-1, resume study drug(s) only if local immunosuppressive therapy was used. Permanently discontinue ipilimumab/nivolumab if systemic therapy was required. | Urgent ophthalmology referral. Topical corticosteroids, cycloplegic agents, systemic corticosteroids. May resume vopratelimumab once off systemic corticosteroids, which are purely indicated for ocular adverse effects or once corticosteroids for other concurrent systemic irAEs are reduced to :S 10 mg; continued topical/ocular corticosteroids are permitted when resuming vopratelimumab to manage and minimize local toxicity |
| | Grade 3 or 4 | 
 Permanently discontinue study drug(s). | Emergent ophthalmology referral. Systemic corticosteroids (IV prednisone 1-2 mg/kg or methylprednisolone 0.8-1.6 mg/kg) and intravitreal/periocular/topical corticosteroids per ophthalmologist opinion |
| Episcleritis | Grade 2 | 
 Temporarily withhold study drug(s) until after ophthalmology consult. | Urgent ophthalmology referral Topical corticosteroids, cycloplegic agents, systemic corticosteroids |
| | Grade 3 or 4 | 
 Permanently discontinue study drug(s). | Emergent ophthalmology referral. Systemic corticosteroids and topical corticosteroids with cycloplegic agents |
| Other | Grade 2 adverse reactions | 
 Withhold study drug(s) until resolved to Grade 0-1. When symptoms resolve to Grade 0-1, resume vopratelimumab only. If symptoms do not recur after 1 cycle of vopratelimumab, resume ipilimumab/nivolumab. If symptoms persist 2' 6 weeks or unable to reduce the corticosteroid dose to less than 7.5 mg prednisone or equivalent per day, subject continuation must be discussed between the Investigator and Medical Monitor | If symptoms persist > 5 days or recur, consider 0.5-1 mg/kg/day prednisone equivalent followed by corticosteroid taper If symptoms persist 2' 6 weeks obtain organ class consultation |

| Adverse Event | Toxicity Grade | Dose Modification | Recommended Management ^a |
|---------------|---|--|---|

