7.1.4.3 Dose Modifications and Toxicity Management for Vopratelimab in Combination with Ipilimumab

For dose modifications for ipilimumab please follow the prescribing information ([Yervoy® Full Prescribing Information {Bristol-Myers Squibb Company 2021}](#)). In the event of a toxicity that requires that study treatment be withheld until resolution to Grade 0 or 1, the first administration of study drug after resolution of toxicity should be vopratelimab alone. Ipilimumab may then be added in sequence at the next dose, at the investigator's discretion, if the toxicity does not recur with vopratelimab monotherapy.

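### Protocol Sections 7.1.4.2 and 7.1.4.3 let nivolumab or ipilimumab return after a hold to Grade 0-1, although Table 1 stops the partner drug permanently after Grade 3 rash

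*Protocol*

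**What the plan says.** Section 7.1.4.2 (nivolumab) and Section 7.1.4.3 (ipilimumab) share one restart rule. The trigger in 7.1.4.2 reads "In the event of a toxicity that requires that study treatment be withheld until resolution to Grade 0 or 1", and 7.1.4.3 uses the same condition. No toxicity and no grade is excluded. The first dose after resolution is vopratelimab alone. For nivolumab the text continues "Nivolumab may be added at the next dose, at the discretion of the investigator and the medical monitor, if the toxicity does not recur" on vopratelimab monotherapy. For ipilimumab it reads "Ipilimumab may then be added in sequence at the next dose, at the investigator's discretion", under the same no-recurrence condition. Both sections refer to the prescribing information for partner-drug dose modifications; neither mentions Table 1.

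Table 1 (Section 7.1.4.1) sets actions by event and grade, and its title names all three drugs. For Grade 3 rash it says "Withhold study drug(s) until resolution to Grade 0-1. When symptoms resolve to Grade 0-1, resume vopratelimab only; permanently discontinue ipilimumab/nivolumab". For Grade 2 rash it allows the partner back: "If symptoms do not recur after 1 cycle of vopratelimab, resume ipilimumab/nivolumab". Section 6.1 settles what is being held: "Study drug(s) refer to vopratelimab and any partner drugs administered in the parent study".

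**The concern.** Table 1 draws a line between two grades of rash. After Grade 2 the partner drug may come back once a cycle of vopratelimab has passed without recurrence; after Grade 3 it may not come back at all. The restart rule in 7.1.4.2 and 7.1.4.3 does not see that line. It looks only at whether treatment was held to Grade 0 or 1 and whether the toxicity recurred on vopratelimab alone.

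A site treating a combination subject could reasonably turn to the section headed with that combination and follow it as written. It would then have permission to re-expose a subject to a checkpoint inhibitor after an event for which Table 1 ends that drug. Long-term safety is the primary objective (Section 4.1), but the issue here is the safety of the individual subject. It is not a claim about any estimate or endpoint.

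**Working it through.** No arithmetic beyond counting applies. The check is whether a Table 1 row can meet the add-back trigger and also bar the partner drug.

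**Step 1: does the Grade 3 rash row meet the trigger?** The trigger is a hold of study treatment until Grade 0 or 1. Section 9.1 uses study treatment for vopratelimab with or without the partner drug, and Section 6.1 includes partner drugs among the study drugs. The Grade 3 rash row holds the study drugs until Grade 0-1, so the trigger is met.

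**Step 2: what does each text then allow?** For a Grade 3 rash resolved to Grade 0-1, with no recurrence on vopratelimab alone:

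| Source | Partner drug |
|---|---|
| Section 7.1.4.2 | Nivolumab may be added at the next dose |
| Section 7.1.4.3 | Ipilimumab may be added at the next dose |
| Table 1, Grade 3 rash | Permanently discontinued |

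**Step 3: how many rows are affected?** Seven rows expressly hold the study drugs until resolution to Grade 0-1:

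| Table 1 row | Partner may resume after 1 clean cycle of vopratelimab? | Permanent stop of the partner only? |
|---|---|---|
| Grade 2 diarrhea/colitis | Yes | No |
| Grade 2 pneumonitis | Yes | Conditional |
| Grade 2 hepatitis | Yes | Conditional |
| Grade 2 nephritis | Yes | No |
| Grade 3 rash | No | **Unconditional** |
| Grade 2 neuropathy | Yes | No (its 6-week stop covers all study drugs) |
| Other Grade 2 | Yes | No |

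Six of the seven carry the same restart sequence as 7.1.4.2 and 7.1.4.3. The seventh, Grade 3 rash, is the direct conflict.

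The condition for Grade 2 pneumonitis and Grade 2 hepatitis is "Permanently discontinue ipilimumab/nivolumab if symptoms last 6 weeks or longer". One further row, Grade 2 uveitis/iritis, holds the study drugs and mentions Grade 0-1 in the following sentence, so it matches the trigger by meaning rather than by wording. Its condition is "Permanently discontinue ipilimumab/nivolumab if systemic therapy was required". The total is 1 direct conflict and 2 + 1 = 3 conditional ones.

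Grade 3 diarrhea/colitis and Other Grade 3 are not counted, because there the partner is stopped at once and only vopratelimab is held. Rows that stop all study drugs outright contain no hold to Grade 0-1 and do not meet the trigger.

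**Step 4: does another rule block the add-back?**

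- Sections 3, 7.1.4, 9.1, 9.2 and 9.2.1 require dose or schedule changes to be discussed with the medical monitor. That is a duty to discuss, not a bar.
- Table 1 footnote b requires Grade 0-1 and less than 7.5 mg prednisone or equivalent per day before treatment resumes. It governs when treatment may resume, not whether the partner is barred. In the text available, the Grade 3 rash row carries no marker for it.
- Section 6.1 limits ipilimumab to 4 doses unless further doses are considered with the medical monitor. That does not bar re-challenge within the limit.

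**Step 5: how soon could the partner return?** One dosing interval after the vopratelimab-alone restart. For ipilimumab that is 6 weeks (every-6-week dosing in Section 6.1). For nivolumab it is 3 or 6 weeks, assuming the schedules in Appendices 1 and 2 apply; the parent-study schedule is not in the documents. Time from onset is not estimated, because it depends on resolution and on any steroid taper, which footnote a sets at 4 to 6 weeks at least or per institutional guidelines.

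**The case against.** The strongest reply is that the restart text is permissive. A site that never uses the discretion complies with both rules, so this is a missing exception rather than one text requiring what another forbids. That is fair as a description of the wording, but a permission to do what a mandatory safety rule bars is still a conflict for the person reading it.

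A second reply is that Table 1 is the more specific text and should be read as governing. That is a natural reading, but the documents do not say so. Table 1 is specific by event and grade, while 7.1.4.2 and 7.1.4.3 are specific by regimen. Section 7.1.4.1 introduces the table as covering vopratelimab, although its title names all three drugs.

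Third, the medical monitor stands between the site and any re-challenge: 7.1.4.2 names the monitor, and the general discussion rule covers ipilimumab too. This lowers the practical risk. It does not remove the conflict, because the monitor works from the same text.

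Fourth, the prescribing information might itself bar re-challenge. It is not in the documents, so this cannot be checked, and the finding does not rest on it.

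Finally, the three conditional rows are weaker. For pneumonitis and hepatitis, the add-back and the 6-week stop sit in the same table cell, so a reader of Table 1 would see both. For uveitis/iritis the trigger is met only by meaning. That stands: Grade 3 rash carries the point.

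**Conclusion.** The concern holds. For a Grade 3 rash that resolves to Grade 0-1, Sections 7.1.4.2 and 7.1.4.3 permit the partner drug to return, while Table 1 discontinues it permanently. No text gives Table 1 precedence. The size is one direct conflict and three that arise only when a stated condition is met.

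This rests on reading the hold of study treatment in the two sections as including the Table 1 hold of study drugs, which the usage in Sections 6.1 and 9.1 supports. The number of combination subjects is not stated, so no count of affected subjects or events is offered. The rule should be corrected because it concerns subject safety and the correction is simple.

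**What to change.** In the add-back sentence of both Section 7.1.4.2 and Section 7.1.4.3, add: *unless Table 1 requires permanent discontinuation of the partner drug*. This settles Grade 3 rash and the three conditional rows together.

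Optionally, name both the investigator and the medical monitor in 7.1.4.3, as 7.1.4.2 does. This is alignment only, since discussion with the monitor is already required elsewhere. The clause does not settle precedence between Table 1 and the prescribing information; a sentence on that could go into the same amendment.

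The cost is one clause in each of two sections and a written amendment with IRB/EC approval (Section 13.5). No procedures, visits or subjects are added. The only thing given up is re-challenge discretion that Table 1 already denies.

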7.1.4.3 Dose Modifications and Toxicity Management for Vopratelimab in Combination with Ipilimumab

For dose modifications for ipilimumab please follow the prescribing information ([Yervoy® Full Prescribing Information {Bristol-Myers Squibb Company 2021}](#)). In the event of a toxicity that requires that study treatment be withheld until resolution to Grade 0 or 1, the first administration of study drug after resolution of toxicity should be vopratelimab alone. Ipilimumab may then be added in sequence at the next dose, at the investigator's discretion, if the toxicity does not recur with vopratelimab monotherapy.

7.2 Infusion-Related Reactions

Post-infusion observation is per institutional guidelines. Signs and symptoms of an infusion reaction may include the following: headache, fever, facial flushing, pruritus, myalgia, nausea, chest tightness, dyspnea, vomiting, erythema, abdominal discomfort, diaphoresis, shivers, hypertension, hypotension, lightheadedness, palpitations, urticaria and somnolence. Although unlikely, serious allergic reactions (e.g., anaphylaxis) may occur at any time during the infusion.

7.2.1 Grade 2 Infusion-Related Reactions

In the case of Grade 2 occurrence of signs and symptoms consistent with infusion related reaction, follow institutional protocol and reduce the rate of infusion of vopratelimab to half the initial rate; consider interrupting infusion of vopratelimab if symptoms do not respond to medical intervention. If signs and symptoms resolve with intervention including interruption of, vopratelimab infusion may be restarted at half the initial rate.

7.2.2 Grade 3 Infusion-Related Reactions

In the case of Grade 3 or greater occurrence of signs and symptoms consistent with infusion related reaction, discontinue infusion of vopratelimab.

7.2.3 *Infusion-Related Reaction Prophylaxis*

For subjects who experience a Grade 2 or 3 infusion-related reaction and remain on treatment, institutional practice for prevention of infusion reactions may be followed for all subsequent cycles.

8 WITHDRAWAL OF SUBJECTS

A subject is free to withdraw from treatment at any time for any reason without prejudice to their future medical care by the physician or at the institution. However, subjects who withdraw from treatment should be encouraged to return for the End-of-study visit and complete all safety assessments. If a subject refuses to undergo the End-of-study procedures, the reason for refusal should be fully documented in the subject's eCRF.

The Investigator or Jounce may also withdraw the subject from treatment at any time in the interest of his or her safety. The primary reason for withdrawal must be recorded in the subject's medical record and on the withdrawal form in the eCRF. If a subject is withdrawn for more than one reason, each reason should be documented in the source document and the most medically significant reason should be entered on the eCRF.

The withdrawal of a subject from treatment should be discussed where possible with the Medical Monitor before the subject stops taking study drug. If study treatment is discontinued, the final evaluations will be performed as completely as possible.

The reason for termination, date of stopping study treatment and the total treatment period must be recorded in the eCRF and source documents.

8.1 Criteria for Withdrawal

The Medical Monitor may be contacted on a case-by-case basis if clarification is required. Reasons for withdrawal include:

- Withdrawal of consent by the subject or refusal by the subject to continue treatment and/or procedures/observations;
- In the case of radiographic progression accompanied by clinical progression. However, in the case of radiographic progression where the subject is clinically stable, it is recommended to continue treatment as long as, in the investigator's opinion, the subject is clinically stable;
- Occurrence of unmanageable adverse events (AEs) in the judgment of the Investigator or subject, justifies withdrawal due to its severity, nature, or requirement for treatment, regardless of the causal relationship to study drug;

- Pregnancy;
- If the Investigator feels it is in the subject's best interest to withdraw;
- Other reasons (e.g., significant protocol violation, non-compliance, loss to follow-up);
- Termination of the study by Sponsor.

9 OVERALL STUDY ASSESSMENTS

Duration of participation on this study will be dependent on the amount of time a subject derives clinical benefit. An End-of-study visit will be performed 28 days (\pm 7 days) after the last dose of study treatment.

9.1 Rollover Entry/Cycle 1 Day 1

Enrollment into the rollover study should occur upon exit from the parent study to avoid any interruptions in study treatment administration.

All assessments should be performed prior to vopratelimab dosing, unless otherwise noted.

- Signing of informed consent form.
- Review eligibility criteria to determine whether a subject may enter the rollover study.
- Physical examination.
- Vital signs pre-and post-infusion.
- Weight.
- Serum or urine pregnancy test for women of childbearing potential. The pregnancy test will not be required for women who are surgically sterile or who are greater than 1 year post-menopausal.
- Laboratory assessments including hematology and chemistry; additional laboratory measurements may be performed in accordance with institutional guidelines.
- Pharmacodynamic biomarkers; Collection of samples may be discontinued at any time per the Sponsor's discretion.
- Record ongoing concomitant medications and AEs.
- Study treatment (vopratelimab \pm partner drug) administration on the same dose and schedule as a subject was receiving at the time of discontinuation from the parent study. Study drug administration between the parent and rollover study should be maintained per the dose and schedule on the parent study. Any changes to the dose and schedule of vopratelimab must be in accordance with a dose and schedule previously shown to be safe and well tolerated and must be discussed with the medical monitor. Any changes to the dose and schedule of nivolumab or ipilimumab must be discussed with the medical monitor.

